5.1.3. Baseline and change-from-baseline

5.1.3.1. Extension Baseline

The **extension baseline value** for efficacy and safety is the last valid non-missing assessment that is taken on or after EOT visit in the core study, and prior to first study drug intake in the extension study. Records meeting these criteria in both core or the extension database are considered for extension baseline. Consequently, the extension baseline value may be the pre-dose assessment on Day 1 of the extension study, but it may also be the value at any visit from EOT visit of the core study (EOT/FU1/FU2 or unscheduled visits). In particular, laboratory parameters are not scheduled to be assessed on Day 1 of the extension study, and so (unless there is an eligible unscheduled assessment) the extension baseline for laboratory parameters will be the last value as above observed in the core study.

Specifically, for MRI and PFT variables only, in case of available assessments on extension Day 1, these should be considered as valid assessments for the extension baseline derivation, even if taken after first dose of treatment on Day 1.

In case of multiple ECG or vital signs assessments (for the same subject, visit, parameter) in the core study visits (EOT/FU1/FU2 or unscheduled visits) that should be considered for the purpose of the baseline value derivation, the average of the results should be taken for use as baseline record.

The derived "extension baseline" value is considered a visit and is displayed in the Combined Analysis Period by visit tables, with corresponding change from core baseline to "extension baseline".

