5.3.1.2.1. T1 Gd+ lesions

The following variables are derived at each scheduled visit during the Combined Analysis Period:

- Total number of T1 Gd+ lesions, derived as:
 Number of new T1 Gd+ lesions (T1GdNewR) + number of persisting T1 Gd+ lesions (T1GdR);
- Total number of T1 Gd+ lesions, categorized (0, 1, 2, 3, 4, 5, 6-10, 11+).

In addition, the following analyses will be conducted:

- The cumulative number of Gd+ T1 lesions from core baseline to extension EOS and corresponding number of scans included will be used as derived.
- Absence of Gd+ T1 lesions at each visit: 'Gd+ T1 lesions at each visit' are considered 'absent', if the number of Gd+ T1 lesions at each visit is zero. If > 0 they are considered 'present'. This applies to nominal visit collected in the CRF.
- Absence of Gd+ T1 lesions from Core baseline until extension EOS: Absence of new Gd+ T1 lesions from Core baseline to extension EOT (including all unscheduled scans) is defined 'absent' if the 'number of new Gd+ T1 lesions' at all post-baseline MRI scans up to the extension EOS is zero. This includes all scheduled and all unscheduled visits. If > 0 at any visit it is considered 'present'. The corresponding 'Number of MRI scans' and time to last MRI scan are derived. If no MRI result at the visit is available (based on visit window), the information is considered missing (for lesion free subjects).
- Total volume of T1 hypointense lesions and the change from baseline: Total volume of T1 hypointense lesions (mm3) (variable T1BHVOL) is recorded by the central reader at each visit. The change from Core baseline is derived as the change from total volume of T1 hypointense lesions at Core study Visit 2-Baseline. The change from Extension baseline is derived as the change from last available record of total of T1 hypointense lesions prior to Extension Baseline.
- Proportion of Gd+ T1 lesions at Core Baseline evolving to persistent black holes (PBHs): It is the proportion (%) of 'Number of T1 hypointense lesions (persistent black holes) evolved from T1 Gad.-enhancing lesion at V2 Baseline core study' (variable T1BHV2C) at each scan visit out of the 'Number of Gd+ T1 lesions at Core baseline'.

Note: Gd+T1 lesions are assumed to not enhance for more than 12 weeks. This requires handling of data as follows:

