- Absence of new or enlarging T2 lesions from Core baseline until extension EOS: Absence of new or enlarging T2 lesions from Core baseline to extension EOT (including all unscheduled scans) is defined 'absent' if the 'number of new or enlarging T2 lesions' at all post-baseline MRI scans up to the extension EOS is zero. This includes all scheduled and all unscheduled visits. If > 0 at any visit it is considered 'present'. The corresponding 'Number of MRI scans' and time to last MRI scan are derived. If no MRI result at the visit is available (based on visit window), the information is considered missing (for lesion free subjects).

Total volume of T2 lesions and the change from baseline: Total volume of T2 lesions (mm3) (variable T2VOL) is recorded by the central reader at each visit. The change from Core baseline is derived as the change from total volume of T2 lesions at Core study Visit 2-Baseline. The change from Extension baseline is derived as the change from last available record of total volume of T2 lesions prior to Extension Baseline.

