5.3.1.2.4. Percent Change of Brain Volume from Baseline

Brain volume is recorded by the central reader as normalized brain volume at the baseline visit and at subsequent visits as a percent change relative to the value at the baseline visit. Percent change of brain volume from baseline to subsequent visits is not manually derived but taken directly from the central reader variable at the corresponding scheduled visit.

The following types of percent change of brain volume are assessed in the extension study:

- Percentage change of Brain Volume from Core Baseline
- Percentage change of Brain Volume from Extension Baseline, i.e. from Core study EOT
- Annual percentage change of Brain Volume from Core Baseline to Core study week 108, defined as: percentage change of MRI brain volume assessment at core study week 108 relative to Core baseline / years-of-follow-up. Here the years-of-follow-up is: (Date of MRI brain volume assessment at core study week 108 – randomization date in core study +1)/ 365.25
- Annual percentage change of Brain Volume from Core Baseline to extension EOS, defined as: percentage change of last MRI brain volume assessment relative to Core baseline / years-of-follow-up. Here the years-of-follow-up is: (Date of last MRI brain volume assessment in extension study – randomization date in core study +1) / 365.25.

CONFIDENTIAL - FOIA Exemptions Apply in U.S.

Annual percentage change of Brain Volume at any assessment by visit from Core Baseline to extension EOS, defined as: percentage change of last MRI brain volume assessment by visit relative to Core baseline / years-of-follow-up. Here the years-of-follow-up is: (Date of last MRI brain volume assessment of the visit in extension study – randomization date in core study +1) / 365.25.

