5.3.2.3. Analysis of MRI-related variables

5.3.2.3.1. T1 Gd+ lesions

The total number of Gd+ T1 lesions per visit will be summarized descriptively as continuous data and in categories (anticipated categories: 0, 1, 2, 3, 4, 5, 6-10, 10+), for the Combined Analysis Period on the EXTS.

Descriptive statistics on absence of Gd+ T1 lesions (frequency and percentages of subjects with lesions absent, present) will be presented by visit, and cumulative for absence of Gd+ T1 lesions from Core baseline up to extension EOT will be tabulated. This analysis will be done for combined period using EXTS.

The total number of Gd+ T1 lesions will be analyzed by visit for the Combined Analysis Period on the EXTS using a negative binomial regression model: the response variable is the number of lesions at the respective visit, with core study treatment as a factor and no offset. Mean model-based estimates and corresponding 95% CIs will be presented. The corresponding plots will also be presented.

Total volume of T1 hypointense lesions and the change from core baseline per visit is summarized descriptively based on observed data, for combine analysis period using the EXTS. In addition, total volume of T1 hypointense lesions and the change from extension baseline per visit is summarized descriptively for extension period using EXTS. The total volume of T1 hypointense lesion data will be listed using FAS.

Descriptive statistics of the proportions of Gd+ T1 lesions at core baseline evolving to persistent black holes will be presented by visit in the subset of subjects with Gd+ T1 lesions present at baseline using the EXTS for combined period. Same analysis in relative to extension baseline (i.e. Core study EOT) will be repeated using EXTS during extension period. A listing will be prepared using the FAS.

Gd+ T1 lesions data will be listed on the FAS.

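### The extension-period change in T1 and T2 lesion volume uses a reference-scan rule that does not match the SAP's extension baseline and has no lower time limit

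*SAP*

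**What the plan says.** Section 5.1.3.1 gives the general rule: the extension baseline is the "last valid non-missing assessment that is taken on or after EOT visit in the core study" but before the subject's first extension dose. For MRI and pulmonary function it adds that, where Day 1 assessments exist, "these should be considered as valid assessments for the extension baseline derivation, even if taken after first dose of treatment on Day 1". Section 5.1.3.2 then makes the extension baseline the reference for all analyses over the Extension Analysis Period.

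The lesion-volume derivations use other words. For T2 volume (Section 5.3.1.2.2) the change from extension baseline is the "change from last available record of total volume of T2 lesions prior to Extension Baseline". For T1 hypointense volume (Section 5.3.1.2.1) it is the "change from last available record of total of T1 hypointense lesions prior to Extension Baseline".

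Sections 5.3.2.3.1 and 5.3.2.3.2 plan to report both volumes by visit on the extension set, relative to the extension baseline.

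**The concern.** The SAP has one definition of extension baseline and a second, differently bounded rule for two endpoints that are reported under the same label. The rules differ at both ends of the window. At the early end, Section 5.1.3.1 stops at the core EOT visit, whereas the volume rule accepts any earlier record. At the late end, Section 5.1.3.1 admits a Day 1 scan even after dosing, whereas a record that must precede the baseline may exclude it.

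The early end matters more. The efficacy objectives in Section 1.1.2 include describing the switch from teriflunomide to ponesimod. If a switch-group subject's reference scan dates from core Week 60 or core baseline, lesion-volume change accrued on teriflunomide is counted in the extension-period change. Subjects in the same table column would also have different starting points, and nothing in the table would show it. A programmer has to choose between the two rules, and the document does not say which prevails.

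**Working it through.** There is no planned figure to reproduce. The check sets the two rules against the MRI schedule and then does visit arithmetic.

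**Inputs**
- Core scans: Baseline, Week 60, Week 108 (EOT) (Section 5.3.1.2).
- Extension scans: Weeks 48, 96, 144, 192, 240, plus Week 288 in Ukraine; none on Day 1 (Section 5.3.1.2; Appendix 12, Table 12). Unscheduled scans are possible at any time.
- Time off treatment between studies: the follow-up visit falls 14–22 or 23–37 days after the last core dose (Section 1.2.1). Consent follows within 1 day and the first dose within 7 days of consent (Table 12, note 2). The range is 14 days to 37 + 1 + 7 = 45 days, or 2.0 to 6.4 weeks.
- Assumption: the core EOT scan falls at the last core dose.

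**Which scan each rule selects** (reading the volume rule as the last scan before the extension began)

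| Scans available | Section 5.1.3.1 | Volume rule |
|---|---|---|
| Usable core EOT scan, nothing later | Core EOT | Core EOT |
| Unscheduled scan after core EOT, before Day 1 | That scan | That scan |
| Day 1 scan | Day 1 scan, even after dosing | May be ignored in favour of core EOT |
| No usable scan from core EOT to Day 1; Week 60 available | Missing | Week 60 |
| As above, and no usable Week 60 scan | Missing | Core baseline |

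An unscheduled core scan between these visits would be picked up in the same way by the volume rule.

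**Core time included for a subject whose reference is carried back**
- From Week 60: 108 − 60 = 48 weeks.
- From core baseline: about 108 weeks.

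**Span of the change at extension Week 48**
- Core EOT reference: 48 + 2.0 to 48 + 6.4 = 50.0 to 54.4 weeks, with no core treatment time.
- Week 60 reference: add 48, giving 98.0 to 102.4 weeks. Core share: 48/98.0 = 49% to 48/102.4 = 47%.
- Core baseline reference: add 108, giving 158.0 to 162.4 weeks. Core share: 108/158.0 = 68% to 108/162.4 = 66%.

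**Span of the change at extension Week 240**
- Core EOT reference: 242.0 to 246.4 weeks.
- Week 60 reference: 290.0 to 294.4 weeks. Core share: 17% to 16%.
- Core baseline reference: 350.0 to 354.4 weeks. Core share: 108/350.0 = 31% to 108/354.4 = 30%.

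These are shares of elapsed time for one affected subject. They equal shares of lesion-volume change only if growth is linear, which the SAP does not claim. The effect on a group mean also depends on how many subjects are affected, and the SAP does not give that number.

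The Day 1 discrepancy is smaller. Using core EOT instead of Day 1 moves the reference back by the off-treatment gap, 2.0 to 6.4 weeks.

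**The case against.** The best defence is that the intention is clear and the exposure small. Section 5.1.3.2 fixes the extension baseline as the reference, and the sentences at issue are themselves defining change from extension baseline. Section 1.2 says that enrolled subjects completed the 108-week core treatment period, so the EOT scan was due for each of them. No Day 1 scan is scheduled. The outputs are descriptive and, under Section 2, exploratory. All of this stands and limits the importance of the point. It does not say what happens when the EOT scan is missing or unreadable, and there the two rules give different answers.

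A reader might infer something stronger: that the reference is core Week 60 for everyone. The argument is that Section 5.3.1.2.4 lists "Percentage change of Brain Volume from Extension Baseline, i.e. from Core study EOT", that Section 5.3.2.3.1 uses the same gloss for persistent black holes ("Same analysis in relative to extension baseline (i.e. Core study EOT) will be repeated using EXTS during extension period"), and that Section 5.1.4 calls the extension baseline a derived value and not a nominal visit. If the baseline is the core EOT scan, the last scheduled scan before it is Week 60.

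The wording permits this, but the document as a whole does not support it. Section 5.1.3.1 treats the derived extension baseline as a visit for display, and Section 5.1.4 lists it after core Week 108 and both core follow-up visits, so the last scheduled scan before it in that order is Week 108. The two glosses concern brain volume and black holes, and they show core EOT as the intended MRI reference. Section 5.3.1.2.2 likewise compares new or enlarging T2 lesions at extension Visit 7 with the core Visit 14 EOT scan. A Week 60 reference would also contradict the quantity being defined.

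**Conclusion.** The point holds as a conflict between definitions with limited reach. On the natural reading, most subjects are referenced to the core Week 108 scan under either rule. The conflict affects subjects with no usable scan from core EOT up to the extension start, and any subject with a Day 1 scan.

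For a subject carried back to Week 60, 48 weeks of core treatment enter the extension change: 47–49% of the elapsed time at extension Week 48 and 16–17% at Week 240. For one carried back to core baseline it is about 108 weeks: 66–68% and 30–31%. These figures assume a gap of 14 to 45 days between studies and a core EOT scan at the last core dose. They must not be read as the bias in the group summaries, because the share of subjects affected is unknown. A Week 60 reference for all subjects is a possible literal reading but probably not the intended one, and the conclusion does not rest on it.

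No hypothesis test depends on this. It is a minor correction that removes a programming choice and keeps the lesion-volume tables consistent with the rest of the SAP.

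**What to change.** In Sections 5.3.1.2.1 and 5.3.1.2.2, replace the reference to the last record preceding the extension baseline with: the extension baseline value as defined in Section 5.1.3.1. Add that the change from extension baseline is missing when no such value exists. Do not add a parenthesis naming particular scans: Section 5.1.3.1 also admits follow-up and unscheduled assessments after core EOT, and a shorter list would create a new inconsistency.

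The cost is two sentences and no new data. Subjects without a qualifying scan drop out of the extension-period change summaries for these two volumes. Reporting their number under each table would show how much the choice of rule matters.

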5.3.1.2.3. Combined unique active lesions (CUAL) and cumulative CUAL

The number of combined unique active lesions (CUAL) at each scan visit is defined as the sum of new T1 Gd+ lesions (T1GdNew R) and new or enlarging T2 lesions without gadoliniumenhancement (T2New R) at each scan visit. Categorization of CUAL at each visit is (0, 1-5, 6-10, 11-15, 16-20, 21-25, 26+).

The cumulative number of CUAL from core baseline to extension EOS is defined as the sum of new T1 Gd+ lesions (T1GdNew R) and new or enlarging T2 lesions without gadoliniumenhancement (T2New R) (i.e., without double-counting the lesions) at all post-baseline MRI visits up to the extension EOS. This includes premature EOT scans, if available, and unscheduled scans only if it is the last available scan for the subject. Categorization of cumulative CUAL at each visit is (0, 1–5, 6–10, 11-15, 16-20, 21-25, 26-30, 31-35, 36-40, 41+).

The cumulative number of CUAL from extension baseline to extension EOS is also derived as described above.

The time up to the last MRI (years) included in the above is derived as = Date of last MRI considered in derivation – core randomization date / extension enrollment date + 1 divided by 365.25 days.

Note that CUAL will be calculated at each visit only if baseline Gd+ T1 lesions is available and "New or enlarging T2 lesions" is not missing at that visit. Otherwise the CUAL is set to be missing.

5.3.1.2.4. Percent Change of Brain Volume from Baseline

Brain volume is recorded by the central reader as normalized brain volume at the baseline visit and at subsequent visits as a percent change relative to the value at the baseline visit. Percent change of brain volume from baseline to subsequent visits is not manually derived but taken directly from the central reader variable at the corresponding scheduled visit.

The following types of percent change of brain volume are assessed in the extension study:

- Percentage change of Brain Volume from Core Baseline
- Percentage change of Brain Volume from Extension Baseline, i.e. from Core study EOT
- Annual percentage change of Brain Volume from Core Baseline to Core study week 108, defined as: percentage change of MRI brain volume assessment at core study week 108 relative to Core baseline / years-of-follow-up. Here the years-of-follow-up is: (Date of MRI brain volume assessment at core study week 108 – randomization date in core study +1)/ 365.25
- Annual percentage change of Brain Volume from Core Baseline to extension EOS, defined as: percentage change of last MRI brain volume assessment relative to Core baseline / years-of-follow-up. Here the years-of-follow-up is: (Date of last MRI brain volume assessment in extension study – randomization date in core study +1) / 365.25.

CONFIDENTIAL - FOIA Exemptions Apply in U.S.

Annual percentage change of Brain Volume at any assessment by visit from Core Baseline to extension EOS, defined as: percentage change of last MRI brain volume assessment by visit relative to Core baseline / years-of-follow-up. Here the years-of-follow-up is: (Date of last MRI brain volume assessment of the visit in extension study – randomization date in core study +1) / 365.25.

5.3.1.3. Neurological variables

5.3.1.3.1. CDA: 12/24-week confirmed disability accumulation

A 12/24-week confirmed disability accumulation (CDA) is defined as a 12/24-week sustained increase from the core baseline EDSS score, according to the definitions described below, which is confirmed at a scheduled visit after 12/24 weeks. 12/24-week CDA is defined for the Combined Analysis Period only.

Every EDSS score obtained (scheduled or unscheduled) within a 12/24-week window after the first progression should also meet the progression criteria, in order to count a subject as having 12/24-week CDA. The 12/24-Week CDA progression starts on the day of the first sustained increase of EDSS after core baseline.

Core baseline EDSS is defined as the last available EDSS score prior to or on the date of randomization.

In the core study, disability as measured by EDSS is assessed in all subjects at Screening, Baseline, and thereafter at scheduled visits every 12 weeks until the end of study. Additional EDSS assessments for individual subjects may have been conducted between scheduled visits (i.e., during an MS relapse).

In the extension study, disability as measured by EDSS is assessed in all subjects at enrollment and thereafter at scheduled visits every 12 weeks until the end of study, as well as at unscheduled visits (during an MS relapse or at any time during the study based on the judgment of the investigator).

CDA is defined as:

- Sustained increase of at least 1.5 in EDSS for subjects with a core baseline EDSS score of 0,
- Sustained increase of at least 1.0 in EDSS for subjects with a core baseline EDSS score of 1.0 to 5.0,
- Sustained increase of at least 0.5 in EDSS for subjects with a core baseline EDSS score \geq 5.5, confirmed after 12 or 24 weeks.

Disability progression can only be confirmed at a scheduled visit, where the EOT and EOS visits count as scheduled visits and can only be confirmed in the absence of a relapse.

Steps to determine 12/24-week CDA

1. All valid post-baseline EDSS assessments (scheduled or unscheduled) will be compared to baseline to assess if the absolute change from baseline meets the CDA criteria, described above. Take the first absolute change from core baseline that meets the criteria for EDSS increase. Onset date of the corresponding potential 12/24-week CDA is the EDSS assessment date.

2. Confirmation of the 12/24-week CDA:

- Partial relapse start date: If only day is missing, consider the relapse has started on the last day of the month (or on relapse end date 1 day if earlier) and ended 60 days later or at (upper limit of a partial) relapse end date, if earlier. If the month or year are missing the relapse does not lead to non-consideration of an EDSS assessment.
- Missing relapse start date: Corresponding relapse does not lead to non-consideration of an EDSS assessment. Do not consider imputed relapse start dates.

5.3.1.3.2. Time to first 12 or 24-week CDA

Time to first 12- or 24-week CDA is defined as start date of the first 12- or 24-week CDA – date of randomization in the core study + 1 in days.

For a subject without a 12- or 24-week CDA, the censored time to 12- or 24-week CDA is defined as:

date of last EDSS assessment without an EDSS increase for subjects without a CDA (as defined above) – date of randomization in the core study + 1.

Subjects without post baseline assessment (without EDSS increase) are censored on randomization date. For subjects without baseline EDSS score missing values are assigned.

5.3.1.3.3. Change from baseline in EDSS

Absolute change from baseline in EDSS score by visit is derived, based on the overall EDSS score as reported by the investigator in the eCRF.

• The change from baseline in EDSS score will be calculated both for the Combined and the Extension Analysis Periods, using the core baseline for the Combined Analysis Period and the extension baseline for the Extension Analysis Period.

